Figure 1-10:	Part 2: SW480 Human Colon Carcinoma Xenografts Grown in NCr Nude Mice.42	
Figure 1-11:	Part 3: SW480 Human Colon Carcinoma Xenografts Grown in NCr Nude Mice.42	
Figure 1-12:	Part 4: SW480 Human Colon Carcinoma Xenografts Grown in NSG Mice	43
Figure 3-1:	Study Schematic	57
Figure 3-2:	3+3 Study Design	59
Figure 4-1:	Study Flow Diagram	66
Figure 6-1:	Investigational Product - Vial Label	82
Figure 6-2:	Investigational Product - Syringe Label.....	83
Figure 6-3:	Investigational Product - Kit Label	83
Figure 7-1:	Visual Analog Scale	100

LIST OF ABBREVIATIONS

Abbreviation	Term
AE	Adverse Event
ALP	Alkaline Phosphatase
ALT	Alanine Aminotransferase
AST	Aspartate Aminotransferase

Abbreviation	Term
BUN	Blood Urea Nitrogen
C _{max}	Maximal Concentration
cART	Combination Antiretroviral Therapy
CBR	Clinical Benefit Rate
CCL5	C-C Chemokine Ligand Type-5
CCR5	C-C Chemokine Receptor Type-5
CFR	Code of Federal Regulations
CHO	Chinese Hamster Ovary
CNS	Central Nervous System
CrCl	Creatinine Clearance
CRF	Case Report Form
CRO	Contract Research Organization
CS	Clinically Significant
CTC	Circulating Tumor Cells
CTCAE	Common Terminology Criteria for Adverse Events
DAPI	4,2-diamidino-2- phenylindole dihydrochloride
DFS	Disease Free Survival
DLT	Dose Limiting Toxicities
DSMB	Data Safety Monitoring Board
ECG	Electrocardiogram
ECL2	ExtraCellular Loop 2
ECOG	Eastern Cooperative Oncology Group
eCRF	Electronic Case Report Form
EOT	End of Treatment
ER	Estrogen Receptor
FDA	U.S. Food and Drug Administration
FI	Fluorescent Intensity
FISH	Fluorescence in Situ Hybridization
FOCBP	Females of Child-bearing Potential
FUV	Follow-up Visit
GCP	Good Clinical Practice

Abbreviation	Term
GMP	Good Manufacturing Practice
HDR	Homology-Directed DNA Repair
HEENT	Head, Ears, Eyes, Nose, and Throat
HER2	Human Epidermal Growth Factor Receptor-2
HIPAA	Health Insurance Portability Accountability Act
HIV-1	Human Immunodeficiency Virus Type 1
IA	Interim Analysis
ICF	Informed Consent Form
ICH	International Conference on Harmonization
IEC	Independent Ethics Committee
IHC	Immunohistochemistry assay
IND	Investigational New Drug
IP	Investigational Product
IRB	Institutional Review Board
ISR	Injection Site Reactions
ITT	Intent-to-Treat
IV	Intravenous
LAR	Legally Authorized Representative
LTF	Lost to Follow-up
mAb	Monoclonal Antibody
MTD	Maximum Tolerate Dose
Nt	N terminus
OBT	Optimized Background Therapy
ORR	Overall Response Rate
OS	Overall Survival
OTC	Over the Counter
PFS	Progression Free Survival
PI	Principal Investigator
PK	Pharmacokinetics
PP	Per Protocol
PR	Progesterone Receptor
RECIST	Response Evaluation Criteria in Solid Tumors

Abbreviation	Term
RP2D	Recommended Phase II Dose
SAE	Serious Adverse Event
SAP	Statistical Analysis Plan
SC	Subcutaneous
SD	Stable Disease
SLD	Sum of the Longest Diameters
SOP	Standard Operating Procedure
SV	Screening Visit
TEAE	Treatment Emergent Adverse Event
TNBC	Triple Negative Breast Cancer
TTNM	Time to New Metastasis
TV	Treatment Visit
VAS	Visual Analog Scale
VF	Virologic Failure

1 INTRODUCTION AND BACKGROUND

1.1 STATEMENT OF INTENT

The design, conduct and reporting of this study shall be conducted in compliance with the protocol, International Conference on Harmonization/Good Clinical Practice (ICH/GCP), and all appropriate regulatory requirements. Investigator(s) participating in this study will have documented training in GCP. Independent monitoring of the trial will be accomplished utilizing a Contract Research Organization (CRO).

1.2 BACKGROUND OF THE DISEASE

1.2.1. Triple Negative Breast Cancer (TNBC)

[figure not shown]
Clinical and molecular heterogeneity of breast cancer are translated in a diversity of clinical patterns of disease evolution and patient outcomes [Dawood, 2011] [Engstrom, 2013] [Harbeck, 2016]. TNBC is defined by the lack of estrogen receptor (ER), progesterone receptor (PgR) and human epidermal growth factor receptor-2 (HER-2) expression, which are known targets of endocrine therapies and anti-HER2 agents, respectively. Chemotherapy is still the main treatment option for TNBC patients. It accounts for 15-20% of breast cancer patients, a clinically highly relevant patient group that is characterized by younger age, unfavorable histopathological features including high histological grade, elevated mitotic count, high rate of p53 mutations and pushing margins of invasion with a shortened overall survival (OS) and disease free survival (DFS) compared to other breast cancer subgroups [Dawood, 2011] [Engstrom, 2013][Malorni, 2012]. For these reasons, TNBC account for a disproportionately high percentage of metastases, particularly distant recurrence, and death among patients with breast cancer. Moreover, in younger women TNBC has been described to occur more often with a high risk of recurrence and death, respectively, the latter with a peak incidence of 3 years after primary diagnosis. The pattern of recurrence involves more often visceral organs and less common bones compared to other breast cancer subtypes [Foulkes, 2010].

1.2.2. C-C Chemokine Receptor Type-5 (CCR5)

The process of cancer cell metastasis in different organs is a complex biologic event. Each tumor type presents a unique pattern of dissemination that has been well recognized for over a century as the “soil and seed” hypothesis [Paget, 1889]. However, only recently factors involved in this process have started to be understood. Preclinical and clinical data have suggested that chemokine receptors and its ligands, also referred as chemoattractant or chemotactic cytokines, are involved in the process of cancer cells tropism by specific organs [Moser, 2001][Neagu, 2015][Velasco-Velazquez, 2012][Chow, 2014]. Studies have correlated the altered expression of C-C Chemokine Ligand type-5 (CCL5) with disease progression in patients with breast cancer [Luboshits,

1999][Niwa, 2001][Zhang, 2009]. Immunofluorescence staining techniques are well established for CCR5 expression. Velasco-Velazquez et al have evaluated an analysis of a combined microarray database comprising 2,254 breast cancer samples and showed that expression of CCL5/CCR5 is higher in basal subtypes (over 58% of samples) of breast cancer compared to luminal subtypes [Velasco-Velazquez, 2012].

Figure 1-1: CCR5 over-expression correlates with poor survival). Immunohistochemical staining for CCR5 in 537 patients

[figure not shown]

CCR5 is also associated with programmed death-ligand 1 (PD-L1) [Halama, 2016]. Anti-PD-L1 antibodies have shown outstanding efficacy in the clinic for melanoma, non-small cell lung cancer and other cancers [Moser, 2001] [Garon, 2015] [Borghaei, 2015][Brahmer, 2015][Larkin, 2015]. Upregulation of PD-L1 may allow cancers to evade the host immune system and also inducing apoptosis in activated T cells. Preclinical data have shown that PD-L1 present in cancer is correlated with CCR5 abundance. Thus, blocking CCR5 may also contribute to increased immune response against tumor cells.

CCR5 has been shown to be sufficient to induce *in vitro* invasiveness and metastasis of breast cancer cells that is blocked by CCR5 inhibitors. Two distinct CCR5 inhibitors (Maraviroc, Vicriviroc) blocked CCR5 signaling and thereby blocked cells migration, invasion and metastasis in mice (Figure 1-2) [Velasco-Velazquez]. The CCR5 inhibitors were shown to block homing of breast cancer cells to the lungs. The dose of CCR5 inhibitor used in these mouse models was the same as the dose used in patients for HIV treatment. Preclinical studies have also demonstrated that oncogenic transformation of immortal human breast cancer cells, with either Ha-Ras, c-Myc, ErbB2

(NeuT) or c-Src, induces the mRNA expression and protein abundance of CCR5 during the process of transformation [Velasco-Velazquez].

Figure 1-2: The CCR5 antagonist Maraviroc inhibits lung metastases in vivo

Another cancer hallmark that CCR5 presents potential role is the DNA repair pathways. This cancer characteristic attenuates apoptosis and contributes to chemotherapy resistance and tumor cells immortality. Preclinical data have separated CCR5+ vs CCR5- SUM159 cells by FACS and conducted mRNA gene expression profiling. GO term pathway analysis demonstrated CCR5+ cells induced the expression of pathways governing DNA repair. QT- PCR was used to quantitate a number of these genes and showed endogenous CCR5 enhances expression of the DNA repair genes, (FANCB, LIG3, POLE and CRY1) governing both homologous and non-homologous DNA repair, nucleotide excision repair and base excision repair. SUM159 cells stably transfected with CCR5 or control vector were compared for the DNA damage/repair response. γ -radiation of SUM159 cells induced p- γ H2AX, however CCR5-overexpressing cells showed reduced p- γ H2AX at 24 hours. Treatment of SUM159 cells with the DNA intercalating anthracycline doxorubicin induced γ H2AX phosphorylation, and CCR5-overexpressing cells showed less p- γ H2AX than its control with 24 hours treatment. The DNA repair reporter, DR-GFP is used to measure homology-directed DNA repair (HDR). In order to measure HDR activity CCR5+ SUM159 cells, the cells were co-transfected with the plasmid encoding I-SceI and the I-SceI based DNA repair reporter DR-GFP

and stained with APC labeled anti-CCR5 antibody. GFP⁺ cells, generated by HDR of I-SceI induced double-strand DNA, were sorted by FACS into CCR5⁻ and CCR5⁺ populations. The percentage of DR-GFP⁺ cells was increased in CCR5⁺ or CCR5⁻ overexpressing cells compared with CCR5⁻ or vector control cells [Robert, 2015]. The dramatic enhancement of DNA repair signaling by CCR5 activation may contribute to the resistance of a patient's tumor to chemotherapeutic agents.

1.2.3. Circulating Tumor Cells (CTCs) in Metastatic Breast Cancer (MBC)

The major treatment objectives in the advanced stage disease remain palliation of symptoms and improvement of quality of life. Importantly, breast cancer is a heterogeneous disease and long-term patient outcome can be influenced by various biological features, as well as by the extent and site of metastatic disease. Typically, widespread visceral disease is associated with symptomatic progression leading to deterioration of the performance status and short survival. Various molecular markers and blood-based tests have been investigated as surrogate for more aggressive disease, among them the most reliable appears enumeration of circulating tumor cells [Xuanmao, 2015].

[figure not shown]
During the last decade, several techniques capable of detecting and quantifying circulating tumor cells (CTCs) in cancer patients have been developed. It has been proposed that subpopulation of CTCs with tumor initiating potential act as a central mediator of metastatic dissemination, giving rise to the formation of distant micrometastases, which subsequently generate overt detectable and frequently measurable lesions [Foulkes, 2010]. In support of this theory, multiple studies have shown that a number of CTCs higher or equal than 5 per 7.5 mL of blood, evaluated before starting systemic treatment, is associated with poor outcome in patients with metastatic breast cancer [Xuanmao, 2015]. In addition, high CTC counts are associated with greater metastatic tumor burden, expressed as number of metastatic sites [Moser, 2001][Neagu, 2015]. Importantly, despite this association, the prognostic value of CTCs is independent from the initial number of metastatic sites [Moser, 2001][Neagu, 2015]. Moreover, a recent pooled analysis of 1944 patients was performed confirming those data [Cristofanilli, 2004]. The authors created a clinicopathological prognostic model to determine the added impact of CTCs for PFS and OS. They found that adding CTC count (<5 or ≥5) to their predictive model significantly increased the prognostication for OS and PFS. The prognostic value of CTCs was consistent across all subtypes of disease. Finally, in the multivariate analysis, CTC count was the strongest prognosticator for PFS and OS. Furthermore, continued elevation of CTCs is known to be associated with a poor prognosis as well as a sign of chemoresistance [Bidard, 2014].

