8.6.2. Covariates

For efficacy analyses, the baseline values will be used as covariates in the analysis models. Other important prognostic factors will be specified in the SAP for the study.

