7.4 Sensitivity Analysis

There will be no sensitivity analysis for this Phase Ib/II study.

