7.7 Covariates and Prognostic Factors

No covariates are planned for this study.

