7.8 Stratification Factors and Subgroups

There are no stratification factors or subgroups for this trial.

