8.3.6 Exploratory Outcome Measures

8.3.6.1 Measure immune biomarkers (PD-L1) in CTCs, metastatic tissue and immune cells such as CAMLs and correlate with therapeutic benefit (PFS)

Immune biomarkers (PD-L1) in CTCs, metastatic tissue and immune cells such as CAMLs will be related to PFS using Cox regression.

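### The exploratory Cox model of CTC PD-L1 on PFS has no defined marker and no covariates, so under several codings that the SAP permits a marker with no effect of its own is biased toward looking prognostic

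*Protocol*

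**What the plan says.** - **Analysis.** SAP 8.3.6.1: "Immune biomarkers (PD-L1) in CTCs, metastatic tissue and immune cells such as CAMLs will be related to PFS using Cox regression". It does not say whether PD-L1 on CTCs means any positive cell, a number of positive cells, a fraction or an intensity. Blood is drawn at baseline, on Day 1 of each later cycle and at end of treatment; the section does not say which sample enters the model or how a patient with no CTCs is classified.
- **Covariates.** SAP 7.7: "No covariates are planned for this study". Protocol 8.6.2 says the opposite: "For efficacy analyses, the baseline values will be used as covariates in the analysis models". It adds: "Other important prognostic factors will be specified in the SAP for the study". The SAP names none.
- **No other check.** SAP 7.8: "There are no stratification factors or subgroups for this trial". SAP 7.4: "There will be no sensitivity analysis for this Phase Ib/II study".
- **Prognostic role of the count.** Protocol 1.2.3, describing a pooled analysis of 1944 patients, reports that "adding CTC count (<5 or ≥5) to their predictive model significantly increased the prognostication for OS and PFS" and that "in the multivariate analysis, CTC count was the strongest prognosticator for PFS and OS". It also links high counts to greater metastatic burden. It gives no hazard ratio.
- **Availability.** Baseline CTC enumeration is already planned (SAP 8.3.4).

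**The concern.** PD-L1 on CTCs can be scored only where there are CTCs, and the chance of finding a positive cell, or the number found, rises with the total. If that total is itself strongly prognostic, an unadjusted hazard ratio for the marker mixes PD-L1 status with tumor-cell load. The trial could then report that PD-L1+ CTCs go with shorter PFS on leronlimab plus carboplatin when the data show only that patients with more CTCs progress sooner. SAP section 5 calls the study hypothesis generating, so the risk is that it generates the wrong hypothesis. This arises at baseline and is separate from any problem with serial samples.

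**Working it through.** The documents give no hazard ratio, event count or power for this analysis, so there is no figure to reproduce. The check asks what the model returns when PD-L1 has no effect.

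**Step 1: detection depends on the count.** If each cell is PD-L1+ with probability p, independently of outcome, a patient with c CTCs has at least one positive cell with probability 1 − (1 − p)^c.
- p = 0.1: 10% at 1 cell, 41% at 5, 88% at 20.
- p = 0.3: 30% at 1 cell, 83% at 5, over 99% at 20.

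**Step 2: a hand approximation.** Take an assumed negative binomial count with mean 15 and k = 0.35, so that 50% of patients have 5 or more CTCs and 27% have none. With p = 0.1 the any-positive marker is present in 79% of patients with 5 or more and in 9% of the rest.
- Share with 5 or more among marker-positive patients: 0.5 × 0.79 / (0.5 × 0.79 + 0.5 × 0.09) = 0.395 / 0.44 = 0.90.
- Among marker-negative patients: 0.5 × 0.21 / (0.5 × 0.21 + 0.5 × 0.91) = 0.105 / 0.56 = 0.19.
- If 5 or more CTCs doubles the hazard, the ratio of average hazards at the start is (1 + 0.90) / (1 + 0.19) = 1.60. The simulation below gives 1.61 for this setting.

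**Step 3: simulation.** From the documents: n = 30, median PFS about 5 months, cut-off at 5 CTCs. Assumed: exponential PFS censored at 24 months (about 28 events); two count distributions (the one above, and mean 30 with k = 0.4, giving 63% at 5 or more and 18% at zero); p of 0.1 and 0.3; hazard stepping up at 5 CTCs; two-sided 0.05. The marker is any PD-L1+ CTC, with a true own effect of 1.0.

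| Assumed CTC HR (≥5 vs <5) | Unadjusted HR, large sample | p < 0.05 at n = 30 | HR adjusted for ≥5 |
|---|---|---|---|
| 1.0 | 0.99–1.01 | 5–6% | 0.98–1.02 |
| 1.5 | 1.31–1.37 | 10–12% | 0.98–1.01 |
| 2.0 | 1.61–1.74 | 21–24% | 0.99–1.03 |
| 2.5 | 1.87–2.02 | 30–34% | 0.98–1.03 |
| 3.0 | 2.07–2.28 | 40–45% | 1.00–1.02 |

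Allowing the hazard to rise with log count instead of stepping at 5 extends the range for a CTC HR of 1.5 to 2.5 to about 1.3–2.2.

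**Step 4: other codings** (CTC HR 1.5 to 3.0).
- Number of positive cells: HR 1.09–1.38 per doubling (of count + 1); p < 0.05 in 12–59% of trials.
- Fraction positive, zero-CTC patients set to 0: HR 1.27–1.74 from 0 to 1; p < 0.05 in 9–24%.
- Fraction positive among patients with at least one CTC, unadjusted: HR 0.94–1.06 (0.92–1.11 over a wider set of assumptions); p < 0.05 in 7–13%.
- Any positive, zero-CTC patients dropped: HR about 1.25–1.8 for a CTC HR of 1.5 to 2.5. At n = 30 with p = 0.3 (mean 20, k = 0.3), p < 0.05 in about 5%, 10% and 14% for CTC HRs of 1.5, 2.0 and 2.5.

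**Step 5: is the ≥5 covariate enough?** The last column of the table is favorable by construction, because the simulated hazard steps exactly where the covariate does. If the hazard rises with log count, adjusting the any-positive marker for ≥5 still leaves HR 1.08–1.41.

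**The case against.** **The SAP never adopts a biased coding.** True. With the fraction among patients who have CTCs there is almost no bias even unadjusted, so it cannot be said that the planned hazard ratio is confounded. What stands is that the SAP permits the biased codings equally and fixes nothing before the data are seen.

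**SAP 7.3 forbids imputation, so zero-CTC patients drop out.** This holds if a zero-CTC sample counts as missing. It could equally be recorded as an observed absence of PD-L1+ cells, and the rule does not say which. Dropping these patients shrinks the problem but leaves HR about 1.25–1.8.

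**It is exploratory, with no formal testing, and the aim is only to correlate.** The p < 0.05 rates correspond to no planned decision, and an any-positive marker really would be associated with PFS. But the estimate itself would be read as information about PD-L1, and the absence of a test does not change it.

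**Stronger readings a reader might infer, which the documents do not support.**
- That a null marker will look prognostic: with any-positive coding and a CTC HR of 1.5 to 3.0, 55–90% of null trials do not reach p < 0.05.
- That zero-CTC patients have the best prognosis: protocol 1.2.3 separates only <5 from ≥5.
- That the CCR5 and PD-L1 comparison is spurious for the same reason: SAP 8.3.6.2 specifies logistic regression and does not say that its PD-L1 is measured on CTCs.

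**Conclusion.** The concern holds as a bias that the plan allows, not as one that it makes certain. Marker coding and zero-CTC handling are undefined, covariates are excluded, and the protocol both names CTC count as the leading prognostic factor and expects baseline covariates. The conflict between protocol 8.6.2 and SAP 7.7 is plain from the text and needs no assumptions.

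The direction of the bias follows from protocol 1.2.3 and the detection arithmetic. Its size rests on assumed CTC distributions, an assumed per-cell positivity unrelated to outcome, and an assumed CTC hazard ratio; if that ratio is 1.0 there is no bias. The primary PFS estimate is a Kaplan-Meier curve that does not use this marker, and tissue PD-L1 does not depend on CTC count. The change is worth making before database lock, but no primary conclusion depends on it.

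**What to change.** 1. In SAP 8.3.6.1, define CTC PD-L1 at baseline as the fraction of CTCs that are PD-L1+, among patients with at least one CTC. Report zero-CTC patients as not assessable, with their number.
2. Include baseline log(CTC count + 1) as a covariate, with ≥5 versus <5 per 7.5 mL as an alternative. Either form can misfit the true shape, so the fraction coding should carry most of the correction.
3. Take the count from the same named assay as the PD-L1 result: protocol 7.11.1.3 describes two (CellSearch and CellSieve). State the volume, because SAP 8.3.4 reports CTCs per mL while protocol 1.2.3 gives the cut-off per 7.5 mL (5 / 7.5 = 0.67 per mL).
4. Amend SAP 7.7 to allow this covariate and reconcile it with protocol 8.6.2.
5. In SAP 8.3.6.2, if PD-L1 on CTCs is used, use fractions and not counts.

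**Cost.** SAP wording and one model term, from a count already collected. The interval widens and the model loses the zero-CTC patients: at 18–27% zero, 30 × 0.82 ≈ 25 to 30 × 0.73 ≈ 22 remain, with roughly 28/30 of them, about 20 to 23, having events. That supports two terms at about 10 events each, for exploratory use only.

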1.2.4. CCR5⁺ tumor-infiltrating leukocytes

The role of CCR5 blockade of the CCL5-CCR5 pathway in immune control of tumors have been defined in several publications in the peer-reviewed medical literature [Mañes, 2003]. CCR5 on tumor cells especially those that evade local immune control in the primary tumor leads to CCR5 positive circulating tumor cells that have the capability to disseminate and migrate into distant tumor sites again through the CCL5-CCR5 axis. Previous research and current data has also

identified other immune mediated anti-tumor effects from CCR5 blockade [Lanitis, 2017, Halama, 2016]. Previous published reports suggest CCR5 expression on Treg cells which migrate into tumors due to the expression of CCL5 by lymphocytes [de Oliveira, 2017, Del Prete, 2017, Lanitis, 2017]. Tregs are responsible for minimizing or eliminating the anti-tumor effects of CD8 T-cells now restored by blockade of PD-L1/PD-1 by the new class of immune-oncology drugs [de Oliveira, 2017]. Further, blocking CCR5 on tissue associated macrophages (TAMs), one of the major cells in the tumor microenvironment that suppresses the T-cell mediated anti-tumor immune response, restores the anti-tumor activity by re-programming the TAMs [Lanitis, 2017, Walens, 2019]. Data from novel 24-color flow cytometry assay performed on single cell suspensions created with IVD IncellPREP device, confirmed the expression of CCR5 on Tregs from the tumor microenvironment in lung, breast, and bladder cancer samples. This technology or CCR5 immunohistochemistry of biopsies already obtained has allowed to selectively choose patients with CCR5 expression not only on tumor but on intra-tumor immune cells in the tumor microenvironment.

Figure 1-3: Tumor Tregs (Stain with CD4, CD325, CD127, and CCR5)

[figure not shown]

Because of the multitude of different mechanism CCR5 blockade may promote anti-tumor activity, immune control, and metastasis, the inclusion criteria has been expanded to encompass these varied mechanisms that may all lead to improved clinical response.

[figure not shown]
Below are the representative IHC staining images showing high predominance of CCR5 positive tumor infiltrating leukocytes in Triple Negative Breast Cancer tissue samples:

Figure 1-4: IHC staining showing high predominance of CCR5+ tumor infiltrating leukocytes in TNBC (Subject 1)

(A) Subject 1: Representative images of IHC for CCR5

(B) Negative Control CCR5

(C) Positive Control CCR5

[figure not shown]
[figure not shown]
[figure not shown]

Figure 1-5: IHC staining showing high predominance of CCR5+ tumor infiltrating leukocytes in TNBC (Subject 2)

[figure not shown]
(A) Subject 2: Representative images of IHC for CCR5

(B) Negative Control CCR5

(C) Positive Control CCR5

